Post Operative Complications will be recorded during the hospital stay or at clinic follow up visits and include any significant deviation from the normal post-operative course. Transient and permanent complications will be evaluated as part of this trial. At the long term follow up visits at 1 and 2 years, investigators capture long term complications such as bladder neck contracture.

Timing of Data Collection

Follow up visit #1 will occur 7 days +/- 7 following discharge, although as indicated above, pain scores and opioid use will be collected on POD7 regardless of clinic visit day. If the clinic appointment is not on POD7, we will collect this data by telephone or by mail. Timing of catheter

removal will be determined by the surgeon and is not affected by the study. Follow up visit #2 will occur 6 weeks +/- 4 weeks following discharge. Follow up visit #3 will occur 12 weeks +/- 5 weeks following discharge to account for patient availability. Patients will have annual follow-up thereafter and long term complications such as bladder neck contracture (BNC) will be recorded at 1 and 2 years post treatment (+/- 3 months). No other study data will be collected at these long term follow up visits. The specifics of how data will be collected and analyzed for each outcome are listed below.

Duration of Study participation

It is estimated that each patient who enrolls in the study and completes the routine follow-up visits will be participating for approximately two years.

Treatment Methodology and Statistical Considerations

Patients will be randomized by chance to either a 16 French or 20 French catheter in a 1:1 ratio. Subjects will be randomly assigned to either the standard of care or multi-modal group using Microsoft Excel ® randomization function.

A 2 year follow-up was chosen to allow for transient postoperative abnormalities to resolve so that the incidence of both transient and permanent complications can be evaluated.

Statistical evaluation of this study was completed by Axio during protocol development to ensure proper design and statistical power. We will use an ANOVA statistical variance model to test the hypothesis that the 20Fr group will have a higher mean pain score than the 16 French group. Secondary outcomes will also be measured with ANOVA analysis.

Sample Size and Accrual

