We performed a pilot study of 25 patients to assess catheter related pain after transurethral resection of the prostate. Using this data, we calculated an average and standard deviation for catheter related pain of 3.2 and 2.45 respectively. In order to detect a difference in pain score of 0.6 between groups, at a power of 80% and alpha of 5%, we determined 44 patients should be included. Predicting a dropout rate of 20%, we plan to enroll approximately 55 patients to achieve 44 patients with full participation.

Data Monitoring

The Clinical Research Program will assess the risk of this trial and will devise and implement an internal monitoring and/or auditing plan for this trial. This plan will be revised as necessary during the life of the trial based upon a variety of factors, including but not limited to: protocol amendments, staff turnover, enrollment metrics, and compliance issues noted. An interim data analysis at 15 patients will be performed to assess pads per day, pain scores between groups, and assess for any difference in complications. If there is a significant difference in major post-operative complications, or patient safety concerns, the study will be terminated.

Data Analyses

Variables to be included in data analysis include aspects of the patient's history as outlined above. Additionally, operative details such as bladder neck reconstruction, change in technique from the stand running robotic vesico-urethral anastomosis or other significant alterations from the standard RALP approach will be included.

Outliers will be double-checked for accuracy. Subjects lost to follow-up will be included in short-term analysis only. Missing post-op data will be evaluated on a case-by-case basis with likely only long-term data being an issue. Missing operative data will be clarified with the operating surgeon. Any data that are not able to be collected with reasonable efforts will not be considered protocol deviations. Data analysis will specifically include risk ratios with 95% confidence intervals for those factors outlined above.

DATA COLLECTION

Records Keeping

Records and data will be kept using a password protected database. Paper source, including signed Informed Consent Form (ICF), will be stored in a secure location for the duration of the trial and securely archived for 10 years following study closure.

Secure Storage of Data

After data collection only de-identified data sets will be used for analysis and further study.

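### The claimed 80% power to detect 0.6 points with 44 patients is wrong: with the plan's own SD of 2.45 the power is about 12%, and 44 patients can detect only about 2.1 points

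*Combined protocol and SAP*

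**What the plan says.** The primary outcome is the mean catheter-related pain score over postoperative days 5 to 7, with one value per patient on a 1-to-10 scale (Study Purpose and Objectives; Data Collection Procedures).

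The Sample Size and Accrual section draws on a pilot of 25 patients after transurethral resection of the prostate, which gave "an average and standard deviation for catheter related pain of 3.2 and 2.45 respectively". It continues: "detect a difference in pain score of 0.6 between groups, at a power of 80% and alpha of 5%, we determined 44 patients". After allowing for 20% dropout, "we plan to enroll approximately 55 patients to achieve 44 patients with full participation". So 44 is the total across both arms.

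The Treatment Methodology and Statistical Considerations section gives 1:1 allocation and an ANOVA comparison of the two groups. It says that an outside group completed the statistical evaluation "to ensure proper design and statistical power". The sample-size text does not say whether the 5% alpha is one-sided or two-sided.

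**The concern.** A difference of 0.6 points is only about a quarter of the stated SD (0.6/2.45 = 0.245). An effect that small needs hundreds of patients, so 44 looks too low by roughly a factor of twelve.

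No other power statement supports the primary outcome, and the ethics board and readers will take this one at face value. They are told that a true 0.6-point difference would be missed one time in five, when it would be missed about seven times in eight. A null result could then be taken to show that the two catheter sizes hurt equally, although the data would still be compatible with differences well above 0.6 points in either direction.

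**Working it through.** **Inputs.** From Sample Size and Accrual: SD 2.45, difference 0.6 points, power 80%, alpha 5%, 44 evaluable patients in total. From Treatment Methodology and Statistical Considerations: 1:1 allocation (22 per arm) and ANOVA. With two groups, the ANOVA F test is equivalent to the two-sided t-test.

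**Step 1: try to reproduce 44.** The normal approximation for two means is n per arm = 2 × (z₁₋α/₂ + z₁₋β)² × SD² / Δ².

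- 2 × (1.96 + 0.8416)² × 2.45² / 0.6² = 261.7, so 262 per arm and 524 in total.
- The noncentral t gives 262.7, so 263 per arm and 526 in total.
- With 20% dropout, 526/0.8 = 657.5, so about 658 would have to be enrolled.

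The figure of 44 is not reproduced. The dropout step is correct: 44/0.8 = 55.

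**Step 2: power that 44 patients provide.** The standard error of the difference is 2.45 × √(2/22) = 0.739, so 0.6 points is 0.6/0.739 = 0.81 standard errors. Power from the noncentral t on 42 degrees of freedom is 12.5%.

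**Step 3: difference detectable at 80% power.** With 22 per arm the noncentral t gives 0.8646 SD, and 0.8646 × 2.45 = 2.12 points (2.07 by the normal approximation). That is 2.12/3.2 = 66% of the pilot mean.

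**Step 4: expected precision.** The 95% confidence interval half-width is t₀.₉₇₅,₄₂ × SE = 2.018 × 0.739 = 1.49 points.

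**Step 5: alternative readings.**

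| Reading | Power | Other result |
|---|---|---|
| 0.6 points, 22 per arm, two-sided | 12.5% | 526 needed in total |
| 0.6 points, 22 per arm, one-sided | 19.9% | 414 needed in total; detectable difference 1.87 points |
| 0.6 points, 44 per arm, two-sided | 20.6% | 30.7% if one-sided |
| 0.6 points, all 55 retained, two-sided | 14.5% | – |
| 0.6 SD (1.47 points), 22 per arm, two-sided | 49% | 62% if one-sided |
| 2.45 taken as a variance, two-sided | – | 107 needed per arm |

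**Step 6: uncertainty in the SD.** If scores are normal, the 95% interval for an SD of 2.45 estimated from 25 patients is 2.45 × √(24/39.36) to 2.45 × √(24/12.40), or 1.91 to 3.41. Over that range, two-sided power for 0.6 points runs from 17% down to 9%, and the detectable difference from 1.65 to 2.95 points. For the claim to be true with 22 per arm, the SD would have to be 0.6/0.8646 = 0.69.

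**Possible origin (an inference).** A standardised effect of 0.6 gives 2 × (1.96 + 0.8416)² / 0.6² = 43.6, rounded up to 44, per arm. So 0.6 SD may have been written as 0.6 points and a per-arm number carried forward as the total. The documents do not show the calculation, and the finding does not depend on this explanation.

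**The case against.** One reading does come close to 44. If 0.6 is a fraction of the pilot mean (0.6 × 3.2 = 1.92 points) and the test is one-sided, in line with the directional hypothesis, then 22 per arm gives 81.9% power. But the protocol describes "In order to detect a difference in pain score of 0.6 between groups", not a proportion of the mean. The same reading gives only 72% power two-sided, and it would support a claim about 1.92 points, not 0.6.

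Sidedness is a fair point. The plan gives alpha without it and words the hypothesis in one direction. Two-sided is the natural reading of a two-group ANOVA, but it remains an assumption and should be labelled as one. Under a one-sided test the trial would miss a 0.6-point difference about four times in five rather than seven in eight.

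The Data Analyses section says that history and operative variables will enter the analysis, which might reduce residual variance. To bring the SD from 2.45 to 0.69, those variables would have to explain 1 − (0.69/2.45)² = 92% of the variance. That is not credible, and no adjusted model is specified for the primary outcome.

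It is also true that the protocol sets no rule for interpreting a null result, so the misreading is a risk and not a stated intention. Finally, rewording does not give the trial power for 0.6 points. If that is the difference that matters to the sponsor, correcting the text will show that 44 patients cannot address it.

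**Conclusion.** The concern holds. On the plan's own inputs, 44 evaluable patients give 12.5% power for a 0.6-point difference, not 80%, and the required total is understated about twelvefold (526 against 44). The difference detectable at 80% power is 2.12 points, about 3.5 times the one claimed.

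These figures assume a two-sided 5% test (which follows from ANOVA), 22 patients per arm, an SD of 2.45 in both arms, and no variance reduction from covariates. The SD comes from a small pilot in a different operation and may not carry over. Neither the plausible range of that SD nor a one-sided test brings power for 0.6 points near 80%: the highest figure in those two checks is 19.9%. The statement is wrong as written and must be corrected.

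**What to change.** Delete the claim of 80% power for 0.6 points. If the sample size is kept, replace it in Sample Size and Accrual with text along these lines:

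> With 44 evaluable patients (22 per arm), an SD of 2.45 and a two-sided alpha of 5%, the trial has 80% power to detect a difference of 2.1 points (0.86 SD) in mean catheter-related pain. Power for a difference of 0.6 points is about 12%. The primary result will be reported as the mean difference with its 95% confidence interval (expected half-width about 1.5 points). A non-significant result will not be interpreted as excluding a difference of 0.6 points.

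The text should say that the two-sided test follows from the planned ANOVA. Before adopting it, the sponsor should confirm what 0.6 was meant to be: points, SD units or a fraction of the mean.

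The cost is protocol wording only, with no added patients and no change to randomisation or visits. The price is a less favourable stated detectable difference. If the sponsor wants 80% power for 0.6 points, that is a different trial, of about 526 evaluable patients.

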Initially, many surgeons used larger catheters (22Fr) to promote an open anastomosis, but some groups have found this to be associated with fossa navicularis strictures⁷. As a result, most surgeons now leave an 18 or 20 French Foley catheter to drainage for approximately 1 week post-operatively⁷. Interestingly, no study to our knowledge has assessed whether catheter size has an impact on continence, post-operative pain, and long term complication rates such as bladder neck contracture. We would expect urinary flow rates to differ based on urethral or catheter diameter according to Poiseuille's law, and several studies have shown this to be the case⁸.

In this study, we will randomize our RALP patients to either a 16 French or 20 French catheter to assess the effect of catheter size on post-operative catheter pain. Additionally, we will investigate pads per day, urinary flow rates, post-void residual urine volume (PVR), International Prostate Symptom Scores (IPSS) and Quality of Life (QoL) score, as well as long term complications. We hypothesize that patients with a smaller catheter will have improved pain scores and less opioid use. In terms of return to continence, we predict that use of a smaller urethral catheter will decrease flow rates and consequently protect against urinary leakage without higher risk of urinary retention. We expect this group to use less pads per day at the 6 week post-operative visit. We do anticipate a higher risk of bladder neck constriction (BNC) would be expected as well in the long term given the smaller diameter anastomosis.

Study Purpose and Objectives

The purpose of this clinical study is to assess the effect of catheter size on post-operative catheter pain, urinary continence, urinary flow rates, PVR, IPSS and QoL scores, as well as long term complications. The details of data collection are described in the "Data Collection Procedures" section below. Study objectives will be measured by:

Primary Outcome:

- Mean catheter related pain score on POD5-7

Secondary Outcomes:

- IPSS and QoL Scores at 6 and 12 weeks
- Opioid use after discharge until POD7
- Pads per Day at 6 and 12 weeks
- Urinary flow rate at 12 weeks
- PVR at 12 weeks
- Long-term complications at 12 weeks, 1 and 2 years

Risks and Benefits

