- Have a significant deviation from the normal operative protocol such as significant bladder neck reconstruction or conversion to open (these patients will be considered a screen fail during the operation and will not be randomized to a certain catheter size)
- Have a history of pelvic radiation

In addition, patients who have a significant deviation from the normal post-operative course such as pulmonary embolism, myocardial infarction, stroke, or other major complications that are unrelated to study intervention but would impact outcome measures may be excluded from data analysis and further data collection per investigator's discretion.

Patient recruitment

Patients seen in pre-operative consultation by Virginia Mason Medical Center urologists will be assessed by the consulting surgeon for protocol eligibility at the time of consultation. The consent form will be reviewed with the patient in person, or by phone, at least 24 hours prior to surgery to allow time for consideration and questions. Patients may sign the consent anytime in the pre-operative setting before medication has been administered.

Early Termination

Patients may be discontinued from the study, per investigator's discretion, if any of the following conditions are met:

- Catheter remains in place greater than 14 days post operatively
- Lost to follow up (patient cannot be reached to schedule a follow up appointment after 3 attempts)
- Patient withdrawal of consent

Data Collection Procedures

Patient follow-up visits are routine and will occur at approximately 1, 6, and 12 weeks post operatively. Specific time point and methods of data collection are described below:

Post-surgical pain scores will be determined using a visual analog scale (VAS) with patients rating their mean post-operative pain on a scale from 1- No Pain to 10- Worst Possible Pain (Figure 1). Patients will be asked to indicate their pain specifically related to the catheter on this

scale. This information will be collected at POD7 just prior to catheter removal. This will be done in clinic if the appointment is that day or by telephone/mail/email/fax if the patient's appointment is not that day. A post-operative form including the VAS pain scale (Figure 1) and a pre-paid mailing envelop will be given to the patient in their study packet.

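### The loss-to-follow-up rule, read plainly, drops contractures and event-free follow-up recorded before loss from the 1- and 2-year complication analysis

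*Combined protocol and SAP*

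**What the plan says.** The rule in Data Analyses is one sentence: "Subjects lost to follow-up will be included in short-term analysis only". The next sentence adds: "Missing post-op data will be evaluated on a case-by-case basis with likely only long-term data being an issue". The section does not define short-term or long-term analysis, and it names no method for the missing data it expects.

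The affected outcome is listed as secondary in Study Purpose and Objectives: "Long-term complications at 12 weeks, 1 and 2 years". Timing of Data Collection says that "long term complications such as bladder neck contracture (BNC) will be recorded at 1 and 2 years post treatment", with a window of 3 months either side. Data Collection Procedures also has complications recorded in hospital and at clinic visits, and the schedule table marks long-term complications at week 12. A contracture can therefore be on record before a man is declared lost, which Early Termination defines as unreachable after three attempts.

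The analysis methods named are ANOVA for secondary outcomes (Treatment Methodology and Statistical Considerations) and risk ratios with 95% confidence intervals (Data Analyses). No time-to-event method, censoring rule or sensitivity analysis is given. On attrition, Sample Size and Accrual says: "Predicting a dropout rate of 20%, we plan to enroll approximately 55 patients to achieve 44 patients with full participation".

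**The concern.** Admitting lost men to the short-term analysis only puts them outside the long-term one. A man with a contracture recorded at week 12 who cannot be reached before year 1 would then be absent from the 1- and 2-year comparison, event included. A man free of contracture at year 1 and then lost would contribute nothing to the 2-year result. What remains is a proportion among completers.

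The protocol expects more contractures with the smaller catheter, and it chose two years of follow-up so that transient and permanent complications could both be evaluated. If 16 Fr reduces pain, contracture is the outcome to weigh against that gain. In about 55 men, the result can turn on one or two events that the trial has already observed.

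**Working it through.** **1. The plan's own attrition figure.** Inputs: 44 men with full participation and 20% dropout (Sample Size and Accrual). 44 / (1 − 0.20) = 55, which matches the plan. 55 − 44 = 11 men, or 5 to 6 per arm at 1:1. The 20% is not tied to a time point and may include withdrawals and other discontinuations, so 11 is a planning figure and not a forecast of 2-year loss.

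**2. Expected events.** The documents give no contracture rate, so I assume a 2-year risk of 2% to 10%. 55 × 0.02 = 1.1 and 55 × 0.10 = 5.5 events. Suppose lost men carry the same risk and 25% to 75% of their contractures are seen before loss. The rule then discards on average between 11 × 0.02 × 0.25 = 0.06 and 11 × 0.10 × 0.75 = 0.83 events. The average is below one, but each event is a large share of the total.

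**3. Effect of dropping recorded events (assumed counts).** Take an arm of 28 with two contractures at week 12, six men lost between week 12 and year 1, one further contracture at year 1 among those still followed, and no loss or event afterwards. Let k be the number of week-12 contractures among the six lost men.

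- Completers only: (3 − k) / 22.
- Kaplan-Meier: 1 − (26/28) × (1 − 1/n), where n = 28 − 2 − (6 − k) = 20 + k.

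| k | Completers only | Kept until last contact |
|---|---|---|
| 0 | 3/22 = 13.6% | 1 − 0.9286 × 19/20 = 11.8% |
| 1 | 2/22 = 9.1% | 1 − 0.9286 × 20/21 = 11.6% |
| 2 | 1/22 = 4.5% | 1 − 0.9286 × 21/22 = 11.4% |

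The arm has the same 28 men and three recorded contractures in every row.

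**4. Follow-up time discarded.** Assume 11 losses spread evenly over two years. If men are observed continuously until loss, 11 × 1 = 11 of 44 × 2 + 11 = 99 person-years go (11%). If contact is only at nominal visits (weeks 1, 6, 12, 52), mean observed time per lost man is (5×1 + 6×6 + 40×12 + 52×52) / 104 = 3225 / 104 = 31.0 weeks, or 0.60 year. That is 6.6 of 94.6 person-years (7%).

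**5. Loss related to contracture.** Let p be the risk, and l1 and l0 the loss probabilities with and without contracture. The completers' rate is p(1 − l1) / [p(1 − l1) + (1 − p)(1 − l0)]. With p = 10% (assumed), overall loss 20%, and l1/l0 = r, l0 = 0.2 / (0.9 + 0.1r).

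- r = 2: l0 = 0.182, l1 = 0.364, rate 0.0636 / 0.80 = 8.0%.
- r = 3: l0 = 0.167, l1 = 0.500, rate 0.0500 / 0.80 = 6.3%.
- r = 0.5: l0 = 0.211, l1 = 0.105, rate 0.0895 / 0.80 = 11.2%.

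These are shifts in a single rate. In each arm the completers' odds are the true odds times (1 − l1)/(1 − l0). If that factor is the same in both arms it cancels, and the odds ratio is unchanged. The risk ratio named in the plan is not exactly invariant, but it moves little when events are rare. With risks of 10% and 2% and the r = 2 loss probabilities in both arms, the completers' rates are 7.95% and 1.56%, so the risk ratio goes from 5.0 to 5.1.

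**The case against.** The sentence is loose. It could mean that a lost man counts at the time points he reached and not after, and the case-by-case sentence leaves room for discretion. Discarding recorded contractures is therefore an inference from the plain reading; the plan does not spell it out. That stands as a caveat. Even so, the milder reading would not carry a week-12 contracture into the 2-year figure, case-by-case review is not a prespecified method, and no other section restores lost men to the long-term analysis.

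Three stronger conclusions are tempting, and the documents do not support them.

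- A reader might infer that the rule biases the comparison between catheters, or biases it in a known direction. The shifts to 8.0%, 6.3% or 11.2% concern one rate. Bias in the odds ratio would need loss to depend on contracture differently in the two arms, and nothing in the documents shows that.
- A reader might infer a fixed loss of 11% of person-time. The figure is about 7% if contact occurs only at scheduled visits, and both figures borrow a dropout rate that is not stated for two years.
- A reader might picture a contracture at 5 months, or follow-up ending at 18 months. Both fall between the visit windows (12 ± 5 weeks, then 1 and 2 years ± 3 months) and would be known only through unscheduled contact. Week 12 and year 1 are the points at which data would ordinarily exist.

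It is also fair to say that Kaplan-Meier assumes loss unrelated to outcome. It recovers contractures seen before loss and no others.

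**Conclusion.** The concern holds in a limited form. On its plain reading, the rule removes contractures and event-free follow-up already on record from the 1- and 2-year complication analysis, and nothing elsewhere in the plan reverses it. At the planning dropout, up to 11 of 55 men could be affected. With 1.1 to 5.5 events expected at an assumed 2% to 10% risk, dropping one or two observed events can change the contracture comparison materially: in the illustration an arm's rate runs from 4.5% to 13.6%, against 11.4% to 11.8% when men are kept until last contact. The event rates, loss counts and loss ratios are assumptions. The direction of any bias is unknown. The outcome is secondary, and pain on POD5-7 is untouched. The point is worth correcting before long-term data are analysed.

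**What to change.** Replace the sentence in Data Analyses with a rule along these lines:

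> Patients in the analysis population who are later lost to follow-up remain in the long-term complication analysis until last contact. Every bladder neck contracture recorded up to then is counted; patients without one are censored at last contact. Cumulative incidence by arm is estimated by Kaplan-Meier at 12 weeks, 1 year and 2 years with 95% confidence intervals, using the recorded date or visit of diagnosis. The numbers at risk and lost are reported by arm at each time point.

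Define short-term and long-term analysis in the same place. Add a simple sensitivity analysis for loss related to contracture, such as varying by arm how many event-free lost men are assumed to have had one. In the illustration with k = 1, five men are lost event-free, so the arm's rate would run from 3/28 = 10.7% (none of them) to 8/28 = 28.6% (all of them). Referring to the analysis population leaves the discretionary post-operative exclusions in Study design as they are; those are a separate matter.

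The cost is SAP wording and one date or visit field, with no extra visits or patients. Intervals will stay wide, diagnosis times will be approximate because late visits are annual, and contractures never observed before loss remain uncorrected, which is why the sensitivity analysis is needed.
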